### 3.4 STUDY CALENDAR

The protocol study calendar of clinical and laboratory monitoring events is as outlined in [Appendix A](#).

Research assays for anti-TARP antibody and TARP-specific cellular responses will be conducted as outlined in [Appendix E](#).

### 3.5 CRITERIA FOR REMOVAL FROM PROTOCOL THERAPY AND OFF STUDY CRITERIA

A safety visit is required approximately 3-6 weeks following the last dose of study therapy. A telephone follow-up will take place should a patient be unable to travel to NIH for a clinic visit.

#### 3.5.1 Criteria for removal from protocol vaccine therapy

- 3.5.1.1 Persistent failure of autologous ME TARP DC or elutriated monocyte placebo vaccine to meet DTM release criteria as determined by DTM and the Principal Investigator.  
Delay in vaccination beyond timeframes established in section [3.3.2](#)
- 3.5.1.2 Patients experiencing a Grade 3 or greater toxicity outlined in sections [3.3.1.3](#) to [3.3.1.5](#) attributed as possibly, probably or definitely related to ME TARP DC vaccination.
- 3.5.1.3 Completion of protocol therapy (6 doses), including safety visit.

#### 3.5.2 Off-Study Criteria

- 3.5.2.1 Completion of study.
- 3.5.2.2 Removal from protocol vaccine therapy as outlined in Section [3.5.1](#).
- 3.5.2.3 Patient develops evidence of visceral or bony metastatic disease.
- 3.5.2.4 Patients with a calculated PSADT of < 3 months after a minimum of 15 weeks on study or 4 doses of vaccine. Prior to removal from study, PSA check and PSADT calculation should be repeated at the next visit in 3 to 6 weeks from the date PSADT < 3 months is identified for an off-study decision.
- 3.5.2.5 Patients with a calculated PSADT that has decreased by > 50% from their calculated Pre-NIH PSADT on or after 24 weeks on study. Prior to removal from study, PSA check and PSADT calculation should be repeated at the next visit in 3 to 6 weeks from the date PSADT decreased by > 50% is identified for an off-study decision.
- 3.5.2.6 Development of a second malignancy other than basal cell or squamous cell carcinoma of the skin that is amendable to local treatment.

- 3.5.2.7 Patient elects to withdraw from study participation at any time.
- 3.5.2.8 Patient is removed from study by the Principal Investigator or Lead Associate Investigator for reasons other than toxicity e.g. failure to adhere to study visits or due to the presence of an intercurrent medical condition, etc.
- 3.5.2.9 Investigator decision to end the study
- 3.5.2.10 Death

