### 3.3.2 Delay in Vaccination

- 3.3.3 Patients who are unable to receive their vaccine injection as scheduled due to adverse events, toxicity, failed vaccine release criteria or unforeseen personal or medical circumstances and who are otherwise eligible to continue on protocol, may be continued on vaccine therapy provided that their next vaccine is within 3 weeks of the scheduled target date of vaccine. Patients will be advised of their options concerning alternative treatments before proceeding with the completion of their study vaccinations. The reason for the change in vaccination schedule will be documented in the patient's chart. If the delay in the vaccination administration is from cell processing scheduling issues or any other regulatory issues not related to patient's medical condition, delay up to 6 weeks is

allowed from the scheduled target date of vaccine administration. Study weeks will be numbered to match vaccine dose weeks. Study Stopping Rules

The study will be halted pending discussing with the FDA and the NIH Intramural IRB if real time safety assessments in the first six lead-in study subjects include the following:

- One or more of the first three subjects (101-103) experiences a Grade II or greater adverse event designated as possibly, probably or definitely related to vaccination with the exception of local injection site reactions.
- Two or more of the first six subjects (101-106) experience a Grade II or greater adverse event designated as possibly, probably or definitely related to vaccination with the exception of local injection site reactions.

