***Once a subject is taken off study, no further data can be collected.***

### 3.5.3 Off Protocol Therapy and Off Study Procedure

Authorized staff must notify Central Registration Office (CRO) when a subject is taken off protocol therapy and when a subject is taken off-study. A Participant Status Update Form from the web site (<http://home.ccr.cancer.gov/intra/eligibility/welcome.htm>) main page must be completed and sent via encrypted email to: NCI Central Registration Office [[contact]](mailto:[contact]).

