11. An enrollment log will be maintained in the regulatory binder/file that is the only location of personal identifiers with unique subject identification number.

The PI will be responsible for overseeing entry of data into an in-house password protected electronic system (C3D) and ensuring data accuracy, consistency and timeliness. The principal investigator, associate investigators/research nurses and/or a contracted data manager will assist with the data management efforts. All data obtained during the conduct of the protocol will be kept in secure network drives or in approved alternative sites that comply with NIH security standards. Primary and final analyzed data will have identifiers so that research data can be attributed to an individual human subject participant.

All adverse events, including clinically significant abnormal findings on laboratory evaluations, regardless of severity, will be followed until return to baseline or stabilization of event. Serious adverse events that occur more than 6 weeks after the last administration of investigational agent/intervention and have an attribution of at least possibly related to the agent/intervention should be recorded and reported as per sections [Error! Reference source not found.](#) and [7.4](#).

AEs will be documented starting with the first study intervention through 60 days following the last administration of vaccine. Adverse events that are serious need to be recorded after 60 days following the last intervention, only if they are serious and related to the study intervention.

An abnormal laboratory value will be considered an AE if the laboratory abnormality is characterized by any of the following:

- Results in discontinuation from the study
- Is associated with clinical signs or symptoms
- Requires treatment or any other therapeutic intervention
- Is associated with death or another serious adverse event, including hospitalization.
- Is judged by the Investigator to be of significant clinical impact
- If any abnormal laboratory result is considered clinically significant, the investigator will provide details about the action taken with respect to the test drug and about the patient's outcome.

**End of study procedures:** Data will be stored according to HHS, FDA regulations and NIH Intramural Records Retention Schedule as applicable.

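### Section 3.5.2.2 makes every stop of vaccine therapy, including finishing six doses, an off-study event that ends data collection, contrary to the follow-up planned to week 96

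*Combined protocol and SAP*

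**What the plan says.** Three statements in section 3.5 link together.

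- Section 3.5.1 lists reasons for removal from vaccine therapy: persistent release failure, "Delay in vaccination beyond timeframes established in section" 3.3.2, related toxicity of Grade 3 or more, and (3.5.1.3) "Completion of protocol therapy (6 doses), including safety visit".
- Section 3.5.2.2 lists "Removal from protocol vaccine therapy as outlined in Section" 3.5.1 among the off-study criteria, with no exception.
- The closing line of 3.5.2 states: "Once a subject is taken off study, no further data can be collected".

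On timing, dose 6 is due at week 24 (section 3.2) and section 3.5 says "A safety visit is required approximately 3-6 weeks following the last dose of study therapy". Section 3.3.2 lets a delayed patient continue "provided that their next vaccine is within 3 weeks of the scheduled target date of vaccine", or within 6 weeks where the cause is cell processing or regulatory.

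Other sections need data well beyond that point:

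- Section 10 names the week 3-48 slope as a primary endpoint, and Appendix G builds it from nine PSAs, the last two at weeks 36 and 48.
- Both interim rules in section 10 wait for 33 patients with 24-week and 48-week changes.
- Sections 3.2 and 6.1 call for scans at weeks 48 and 96. Appendix G computes slopes to week 96, and section 1.1.2 sets PFS at 96 weeks.
- Section 6.1 states: "AEs will be documented starting with the first study intervention through 60 days following the last administration of vaccine".

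Section 3.5.3 asks staff to notify the registration office "when a subject is taken off protocol therapy and when a subject is taken off-study", so it treats the two as different events.

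**The concern.** Staff hold two current instructions about when data collection ends, and they cannot both be followed. Under 3.5.2.2 as written, nobody who completes vaccination could contribute a week 3-48 slope distinct from the week 3-24 slope, and the interim trigger could not be met.

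The larger practical risk lies with patients who stop vaccine early. Section 10 counts a patient as evaluable after three doses, so they stay in the analysis. Yet no section clearly keeps their PSA visits. The sentence in section 3.2 about all patients presumes six doses, and note 9 of Appendix A offers only annual contact after therapy. Their slopes would be truncated or missing because they stopped, and PSAs not drawn on schedule cannot be recovered later. Whether this would differ between arms is not shown in the documents.

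**Working it through.** **Date of leaving under the literal rule.** These are nominal calendar weeks; section 3.3.2 renumbers study weeks to match doses, so real dates can differ.

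- Completer: week 24 + 3 to 6 = week 27-30.
- Stop after dose 3 (week 9) with prompt removal, for example for toxicity: safety visit at week 9 + 3 to 6 = week 12-15.
- Stop after dose 3 through delay: dose 4 target week 12 + 3 to 6 = about week 15-18.
- Only dose 6 missed through delay: week 24 + 3 to 6 = week 27-30 or later.

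**What is lost for a completer.** Appendix G has 13 on-study PSA points from week 3 to week 96. The six at weeks 36, 48, 60, 72, 84 and 96 fall after week 30. Seven of the nine values for the week 3-48 slope remain, and they are exactly the week 3-24 set. The adverse-event window ends at 24 + 60/7 = week 32.6, which is 60 - 42 = 18 to 60 - 21 = 39 days after the safety visit.

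**Precision of one patient's slope.** For an ordinary least-squares slope with equal, independent errors (an assumption), SE is proportional to 1/sqrt(Sxx), where Sxx = sum of (week - mean week)^2. Hence SE ratio = sqrt(Sxx planned / Sxx available).

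| PSA weeks available | PSAs | Sxx (week^2) | SE relative to planned week 3-24 slope | SE relative to planned week 3-48 slope |
|---|---|---|---|---|
| 3-48, as planned | 9 | 1746.0 | n/a | 1 |
| 3-24 (as planned; also the literal completer) | 7 | 313.7 | 1 | 2.36 |
| 3-18 | 6 | 157.5 | 1.41 | 3.33 |
| 3-15 | 5 | 90.0 | 1.87 | 4.40 |
| 3-12 | 4 | 45.0 | 2.64 | 6.23 |

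For example, 1746.0/313.7 = 5.57 and sqrt(5.57) = 2.36.

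Reading the table by route:

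- Prompt removal after dose 3 leaves 4-5 PSAs: SE 1.9-2.6 times the planned week 3-24 value and 4.4-6.2 times the planned week 3-48 value.
- The delay route after dose 3 leaves about 5-6 PSAs: 1.4-1.9 and 3.3-4.4 times.
- If only dose 6 is missed, the week 3-24 slope can be complete and only weeks 36 and 48 are lost.

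**Stated power.** Section 10 quotes 81% for 44 v 22, a difference of 0.048, SD 0.072 and one-sided 0.05. A noncentral t calculation with effect 0.048/0.072 = 0.667 gives 81.1%, so the figure reproduces and is not in dispute. The SE ratios above are within-patient only and do not carry over to the comparison of arms.

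**The case against.** The strongest reply is that nobody would apply the rule to completers. That stands. Section 3.5.2.1 lists completing the study as its own criterion, 3.5.2.5 applies from week 24 onward and would have almost no scope if completers left by week 30, and every schedule runs to week 96. For completers this is a wording repair.

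A second reply is that early stops should be rare. In the earlier pilot (section 1.2.4) one patient left for vaccine viability and none is listed for toxicity. Taking 1/41 to 1/20 as a rate gives 66/41 = 1.6 to 66/20 = 3.3, or about two to three of 66 randomized patients. This suggests that few may be affected. It is not a rate for this trial, however: the product had two peptides rather than seven, its off-study rules are not given, and no delay category was tabulated.

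A third reply is that the Précis promises restaging at weeks 48 and 96 to all patients, without tying it to dosing. True, but that secures scans, not PSAs.

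Two further points stand as limits. The delay-route counts assume nominal visits continue while dose 4 is pending, which the renumbering of study weeks leaves unclear. And following early stoppers to week 96 meets section 4, which bars other anticancer therapy during the trial, while 3.5.2 has no explicit criterion for starting it.

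**Conclusion.** The contradiction is real on the current text and should be fixed. A stated rule that, followed literally, discards co-primary data is wrong as written rather than merely short of detail. For completers the intended meaning is clear from the rest of the plan, so the practical damage should be small. For early stoppers with at least three doses the rule plausibly operates as written, leaving patients in the analysis while barring collection of their endpoint.

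For those patients the size is the within-patient loss of precision shown above, on nominal weeks and with equal independent errors. No bias, loss of power or imbalance between arms has been demonstrated. How many patients would be affected depends on an early-stop rate that the documents do not give.

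**What to change.** Reconcile sections 3.5.1 to 3.5.3 with Appendices A and G.

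- Reword 3.5.2.2 so that meeting a 3.5.1 criterion takes the patient off vaccine therapy but not off study.
- State that the PSA, imaging, adverse-event and PFS follow-up already scheduled continues to week 96 unless a separate off-study criterion is met, for completers and early stoppers alike.
- Record the start date of any other anticancer treatment, so that later PSAs can be identified in the analysis, and say how the exclusions in section 4 read for a patient who is off vaccine but still in follow-up.

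Dosing, toxicity and treatment-stopping rules, and off-study criteria 3.5.2.3 to 3.5.2.10, are not addressed here and need not change.

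The cost is protocol wording and one recorded date, with no new type of visit. The burden is that early stoppers keep visits already on the calendar, and some of their later PSAs may be affected by other treatment.

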Assuming a common standard deviation of 0.072 (as was approximately found on the TARP arm B in the prior trial), this would mean that detecting an effect size of 0.67 SD ( $0.048/0.072=0.67$ ) could be a reasonable goal. With a 2:1 randomization (2 getting vaccine to 1 getting placebo), with 44 on the active arm and 22 on the placebo arm, there is 81% power to detect a difference between the two arms on the order of 0.048 slope log PSA units, assuming the parameters from the prior study may be approximately true and a 0.05 one-sided significance level is sought. The analysis is assumed to be done with a two- group t-test, while in practice a Wilcoxon rank sum test will be used if the values in the two arms are not normally distributed ( $p<0.05$  by a Shapiro-Wilks test). In addition, although using a 0.05 significance level for each test assumes that a Bonferroni correction will be used to adjust the two tests for multiple comparisons, in practice, a less overly conservative Hochberg test may be used to interpret the results. It should also be noted that since the two primary endpoints involve overlapping intervals of time, the results may not be independent of one another and thus this should factor into the interpretation at the conclusion of the study.

In addition to the two primary endpoints, the change in log slope (PSA) at later time points, such as weeks 48-96, may also be evaluated as a secondary endpoint. As this is a prospective, single-blinded, randomized placebo controlled trial, the NCI/CCR DSMB will be used to monitor the trial. This monitoring will be done for both futility and for efficacy, as well as for safety.

The futility monitoring will be performed as follows: at the first DSMB meeting after which half of the projected patients have been evaluated (33 total patients have been evaluated for both the changes to 24 weeks and the changes to 48 weeks), the slope differences will be calculated on both arms. If at this point, the slope difference for the placebo arm indicates the same or greater benefit compared to that for the active arm, then the trial will not accrue any further patients since the results to date would indicate lack of benefit from using the active vaccine.

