The evaluation for better than expected efficacy will be performed as follows: at the first DSMB meeting after which half of the projected patients have been evaluated (33 total patients have been evaluated for both the changes to 24 weeks and the changes to 48 weeks), the slope differences will be calculated on both arms. If at this point, the one tailed p-value is  $<0.0054$ , then the trial will stop accrual for better than expected efficacy. By using this interim evaluation for monitoring, the final significance level would need to be  $<0.0492$  to declare the result to be significant at the 0.05 level.

Safety and evaluation of other immune parameters will also be included in the analyses, as secondary objectives. These will be explored primarily with descriptive statistics and any comparisons between the two arms will be reported without any formal adjustment for multiple comparisons.

With 66 patients as an objective for the randomized portion of the study ( $N = 44$  ME TARP vaccine and  $N = 22$  elutriated monocyte placebo vaccine) and the initial lead in of 6 patients, a total of 72 patients may be required. In order to allow for a small number of invaluable subjects, the accrual ceiling will be set at 75. For the data collection and analysis, we will define the

evaluable patients as receiving at least 3 doses of vaccines. It is anticipated that up to 2-3 years may be required to enroll 66 patients to the randomized portion of the study.

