### Pre-NIH and On Study PSADT Calculation:

- PSADT will be calculated using the Memorial Sloan-Kettering Cancer Center cancer information prostate nomogram for PSA doubling time found at:  
<http://nomograms.mskcc.org/Prostate/PsaDoublingTime.aspx>.
- Minimum requirements for PSADT include  $\geq 3$  PSA measurements over  $\geq 3$  months.
- The interval between PSA measurements must be  $\geq 4$  weeks.
- For patients receiving 5-alpha reductase inhibitors (5ARI) e.g. finasteride or dutasteride, only PSA values obtained after at least 3 months on therapy may be used to calculate PSADT.
- PSA values used in the calculation of PSADT must have been performed by the same laboratory, when possible.
- All PSA values used in the calculation should be  $\geq 0.2$  ng/mL and follow a rising trend although all values need not be consecutively rising.
- All values obtained over a maximum period of 12 months prior to enrollment will be utilized to calculate the patient's Pre-NIH PSADT.

Date Range of PSA Values (should not exceed 24 months): \_\_\_\_\_

Cumulative Total Months of PSA Values (should not exceed 24 months): \_\_\_\_\_

Receiving Flomax:  YES  NO      Start Date: \_\_\_\_\_ On at least 3 Months:  YES  NO

Receiving 5ARI:  YES  NO      Start Date: \_\_\_\_\_ On at least 3 Months:  YES  NO

DATE	PSA ng/mL	TESTOSTERONE ng/dL	PSADT

Record PSA values with a maximum of 2 digits after the decimal point.

NIH PSA values in blue.

Calculated Pre-Enrollment/Baseline PSADT (in months)/ Slope Log PSA: \_\_\_\_\_

Value is  $> 3.0$  Months and  $\leq 15$  Months:  YES- Eligible

NO- Ineligible for Study

**Study Number:** \_\_\_\_\_

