**Calculated Pre-Enrollment/Baseline PSADT (in months):/ Slope Log PSA:\_\_\_\_\_**

**PSADT/Slope Log PSA will be calculated at Weeks 15, 18, 24, 36, 48, 60, 72, 84 & 96. Calculate using PSAs from both the entire study period and the prior 6 months.**

Date	Study Week #	PSA ng/mL	Testosterone (ng/dL)	PSADT
	0			Value NOT used in calculations
	3			PSADT is not calculated at this point
	6			PSADT is not calculated at this point
	9			PSADT is not calculated at this point
	12			PSADT is not calculated at this point
	15			
	18			
	24			
	36			
	48			
	60			
	72			
	84			
	96			

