**Record PSA values with a maximum of 2 digits after the decimal point.**

PSADT Calculated for Statistical Analysis			
Analysis Window	Study Wk PSA Values Included	PSADT/Slope Log	Percent Change PSADT
Pre-NIH	Time of Entry		
Week 3 to Week 15	Wks 3, 6, 9, 12, 15		
Week 3 to Week 24	Wks 3, 6, 9, 12, 15, 18, 24		
Week 3 to Week 48	Wks 3, 6, 9, 12, 15, 18, 24, 36, 48		
Week 24 to Week 48	Wks 24, 36, 48		
Week 48 to Week 72	Wks 48, 60, 72		
Week 48 to Week 96	Wks 48, 60, 84, 72, 96

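### The PSADT off-study rules end PSA collection because of the primary outcome, Section 10 has no rule for a shortened slope 348, and the only analysis set depends on doses received after randomisation

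*Combined protocol and SAP*

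**What the plan says.** **Removal.** Section 3.5.2.5 removes "Patients with a calculated PSADT that has decreased by > 50% from their calculated Pre-NIH PSADT on or after 24 weeks on study". Section 3.5.2.4 removes patients whose PSADT is under 3 months once they have had 15 weeks on study or 4 doses. Both need a repeat 3 to 6 weeks later. The closing sentence of 3.5.2, directly above 3.5.3, adds "Once a subject is taken off study, no further data can be collected".

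**Endpoints.** Section 10 has two primary endpoints: the week 3-24 slope of log PSA minus the pre-study slope (slope 324), and the week 3-48 slope minus the same pre-study slope (slope 348). The analysis table in Appendix G builds the latter from "Wks 3, 6, 9, 12, 15, 18, 24, 36, 48".

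**Who is analysed.** Section 10 defines "evaluable patients as receiving at least 3 doses of vaccines" and names no all-randomised set. The interim look takes place once "33 total patients have been evaluated for both the changes to 24 weeks and the changes to 48 weeks"; if its one-tailed p-value is below 0.0054, "then the trial will stop accrual for better than expected efficacy".

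**PSADT calculation.** Appendix G states "Minimum requirements for PSADT include" at least 3 values over at least 3 months. For on-study values it says "Calculate using PSAs from both the entire study period and the prior 6 months". Section 3.5.2 does not say which of the two windows triggers removal.

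**Completion.** Section 3.5.1.3 counts completing six doses as removal from vaccine therapy, and 3.5.2.2 makes removal from vaccine therapy an off-study criterion. Appendix A schedules PSA to week 96, and its footnote 9 provides annual follow-up after therapy.

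**The concern.** Section 1.2.4 gives PSADT as ln 2 divided by the slope of log PSA. A PSADT that has more than halved is therefore a slope that has more than doubled. The patients who lose their later PSAs are those doing worst on the primary outcome, and if the vaccine works they will be mostly placebo patients.

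Section 10 does not say whether such a patient's slope 348 is formed from the values in hand or left out. The answer affects one of two primary tests and the interim look, and it would be settled only when the data exist.

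Separately, whether a randomised patient reaches 3 doses depends on later events such as product release failure, delay or toxicity. The comparison is then not fully protected by randomisation.

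**Working it through.** **1. What can be lost.**
- Halving rule flagged at week 24: the repeat falls at weeks 27-30, so weeks 36 and 48 are lost. Flagged at week 36: the repeat falls at weeks 39-42, so week 48 is lost. Slope 324 is already complete in both cases.
- Under-3-months rule flagged at week 15 and confirmed at week 18: slope 324 also loses week 24.
- The 4-dose limb could apply at week 12, because Section 6.1 calculates PSADT at every study time point. Confirmation at week 15 would then also cost week 18. The Appendix G worksheet, however, says PSADT is not calculated at week 12.

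**2. The plan's own figure.** Noncentrality = difference / (SD × √(1/44 + 1/22)), with √(1/44 + 1/22) = 0.2611. For 0.048 and SD 0.072 this is 2.553. A one-sided 0.05 t-test on 64 df then has 81.1% power, matching the stated 81%.

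**3. Slope 348 with complete data.** Section 10 gives the pilot dendritic-cell arm as -0.049, SD 0.062. Its anticipated untreated values, +0.010 to +0.015, are stated for slope 324 and assumed here for slope 348.
- Difference 0.059: 0.059 / (0.062 × 0.2611) = 3.644, power 97.5%.
- Difference 0.064: noncentrality 3.953, power 98.8%.

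**4. Does removal differ by arm?** Take slopes as natural log per month. The halving rule is met when on-study slope > 2 × pre-slope, that is, when the slope difference > ln 2 / baseline PSADT. The chance is 1 - Φ((threshold - mean) / 0.062), ignoring confirmation and timing.

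| Baseline PSADT | Threshold | Active | Placebo (+0.010 / +0.015) |
|---|---|---|---|
| 15 months | 0.0462 | 6% | 28% / 31% |
| 9 months | 0.0770 | 2% | 14% / 16% |

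**5. Simulation with timing and confirmation.** 44 versus 22 patients, PSA at the nine listed weeks, and repeat checks at weeks 28 and 40. Total SD of the slope-348 difference was held at 0.062. There were 24 settings of 3,000 trials, each tested one-sided at 0.05. Assumed: baseline PSADT uniform on 3-15 months, all 8 months, or uniform on the slope scale; log-PSA noise 0 or 0.1; PSADT over the whole study or the prior 6 months.
- Removed before week 48: 1-7% of active and 11-28% of placebo, or 3-10 of 66 patients on average.

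| Handling | Difference | Power |
|---|---|---|
| Full data | 0.058-0.064 | 97-99% |
| Removed patients excluded | 0.044-0.052 (18-27% smaller) | 86-95% |
| Kept on available PSAs | 0.059-0.066 | 97-99% |

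- With equal arms, one-sided error was 4.3-5.7% with exclusion and 4.6-5.5% with full data (simulation error about 0.7 points).
- Interim efficacy stop at 33 patients, slope 348 alone, p < 0.0054: 45-56% with all patients, 26-40% if removed patients are not counted. The closed form with 22 versus 11 gives 46-54%.
- Sensitivity with placebo mean 0: power 90-92% with full data, 75-85% with exclusion.

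**6. Pilot context.** Section 1.2.4 lists 2 of 41 vaccinated patients off study on PSADT criteria (4.9%, exact 95% CI 0.6-16.5%). Follow-up ran to 144 weeks, one exit was at week 9, and there was no placebo arm. This does not calibrate the rates above.

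**The case against.** The strongest reply is that the plan already implies the harmless answer. Evaluability needs only 3 doses, and the third is due at week 9, before either PSADT rule can act. A patient removed after week 24 has seven listed PSAs over 21 weeks, well above the count-and-span minimum in Appendix G. The interim count fixes when the look happens, not who enters the final test. This largely stands: keeping these patients is the better-supported reading. It remains an inference, because neither Section 10 nor Appendix G says what to do with an incomplete series.

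It is also fair that every removal rate here rests on assumptions, and that a lower chance of stopping early for efficacy mainly means the trial continues.

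Stronger readings do not hold:
- A reader might infer a false-positive risk. The equal-arm error rates show none.
- A reader might apply the rules to the sample-size inputs (0.048, SD 0.072) and find power of 57-65% with exclusion. Those inputs belong to slope 324, which is complete when the halving rule acts, and that calculation ignores the confirmation step.
- A reader might say the analysis set is chosen after randomisation. Its definition is pre-specified; only membership depends on later dosing.
- A reader might conclude that follow-up really stops at six doses. Appendix A shows otherwise, so this is a contradiction to reconcile.

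**Conclusion.** The point holds in a limited form. Rules that act on the primary outcome end data collection, and the handling of the shortened slope 348 is not stated. If removed patients are kept on available PSAs, the loss is near zero. If they are excluded, the slope-348 difference is about 18-27% smaller, given the assumed placebo slopes, baseline PSADT spread and PSA noise. That bias is towards no effect, and final power stays above 81% under the plan's placebo values; it fell below 81% in some settings only with a placebo mean of 0, which Section 10 does not anticipate. Slope 324 is nearly untouched.

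The effect of the 3-dose set cannot be sized or given a direction. The conflict of 3.5.1.3 and 3.5.2.2 with Appendix A rests on no assumption: taken literally, slope 348 could not be formed as listed for any patient who completes treatment.

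**What to change.** - **Data collection.** Amend the closing sentence of 3.5.2, and reconcile 3.5.1.3 and 3.5.2.2 with Appendix A and its footnote 9. Coming off vaccine or meeting a PSADT criterion should not end PSA collection at scheduled visits through week 48, unless consent is withdrawn.
- **Primary analysis.** All randomised patients in their assigned arm, with slopes from all available on-study PSAs up to the start of other prostate-cancer therapy. Apply the same rule to the interim count of 33.
- **Sensitivity analysis.** Report the set with at least 3 doses.
- **Optional or clarifying.** A mixed model on log PSA would also cover patients with too few values, but per-patient slopes suffice. Stating which PSADT window triggers removal, and reconciling Section 6.1 with the worksheet on week 12, are clarifications only.

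No treatment or removal rule is proposed here.

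**Cost.** Wording, plus PSA draws that Appendix A already schedules. In the simulation this is up to three per PSADT removal (weeks 24, 36, 48), about 6-23 in total. A patient stopped after one or two doses could need up to eight (weeks 6-48). The downsides are slight dilution from patients with few doses, and fewer recovered values where other therapy starts early.
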